8.2. BASELINE CHARACTERISTICS

8.2.1. Demographics

Subject's demographic information will be collected at the Screening visit and will include initials, date of birth (DOB), sex, and subject-reported race, and ethnicity.

8.2.2. Medical/Surgical History / Prior and Concomitant Medications

Medical/surgical history will be collected at the Screening visit to ensure subjects are eligible for participation in the study (per inclusion Section 7.1 and exclusion Section 7.2 criteria).

The Investigator or designee will collect a complete medical history at the Screening visit, including review of subject's prior and concomitant medications (per Section 9.9). The medical history will include review and recording of dermatological (including RDEB history, history of SCC and any recent skin infections), neurological, ophthalmic (including review of keratitis), ear/nose/throat, cardiovascular, respiratory, gastrointestinal (including review of nutritional deficiencies, anorexia, dysphagia, failure to thrive, need for gastrostomy, constipation, esophageal dilation history, oral pain, and dental issues), hematologic (including history of anemia, hypoalbuminemia, previous treatments including transfusions and iron supplementation), endocrine, renal, hepatic, psychiatric and other conditions/diseases (such as history of bone pain), as well as allergies (drug, food, environmental).

The Investigator or staff must record all clinically or medically relevant information as medical history.

8.2.3. Skin Biopsy for FCX-007 Manufacturing

Three (3) 3-4 mm skin biopsies for the purpose of FCX-007 manufacturing will be collected at the first Screening visit if not previously obtained in a prior FCX-007 study (i.e., FI-EB-001). Biopsies will be collected from subject's normal/unaffected/intact skin with the specific location varying on a case-by-case basis based on the Investigator's judgment (refer to Appendix 1 for additional collection site guidance).

An additional set of skin biopsies may be collected if the manufacturing process does not yield an FCX-007 cell count sufficient for at least one treatment session or does not meet release specifications.

Biopsy collection procedures are provided in Appendix 1. Additional details regarding biopsy supply requisition, scheduling, collection, preparation and shipment of the biopsies to Castle Creek will be detailed in the Study Procedures Manual, as applicable.

8.3. EFFICACY ASSESSMENTS

8.3.1. Wound Assessments by Unblinded and Blinded Investigators

Screening and Baseline assessments necessary for identification, mapping, selection, and labeling of wounds are to be performed by the PI, or trained, medically qualified Sub-I, who will remain unblinded to wound treatment assignment throughout the study.

The Investigator Assessment of Complete Wound Closure of Target Wounds must be performed by a Blinded Investigator at at Weeks 12, 22, and 24 (Table 3). Blinded assessment is also preferred at Weeks 36 and 48.

At all Long-Term Follow-Up visits, the Investigator Assessment of Complete Wound Closure by remote video assessment is encouraged but optional for **treated** Target Wounds (treatment wound), the wounds originally designated as control should not be assessed. This assessment should occur only if the treated Target Wound was closed at Week 48 (Month 12/Year 1) and should cease at further visits if the treated Target Wound is open at any Long-Term Follow-Up visit.

This assessment is to be completed after removal of subject's dressings from target wound pairs (treatment and control wounds) **and prior to any potential disruption of the target wounds** (i.e., surgical pen markings, target wound tracing, bacterial culture of wounds if applicable, FCX-007 administration preparation or administration, or collection of biopsies).

The Blinded Investigator will not have access to the subject's source documents, CRFs, or electronic data capture (EDC) as information regarding target wound randomization and treatment information is available. The Blinded Investigator's assessments will be maintained as separate source documents and stored in a separate location. Written or verbal communication about treatment assignment or interval changes in wounds between those involved in administering FCX-007 (including study team members, subjects and those accompanying subjects at any visit, or others who have knowledge of the wound treatment assignment) and the Blinded Investigator will be discouraged, and a verbal reminder of this requirement will be stated by the Blinded Investigator at the time of the assessments.

8.3.1.1. Potential Target Wound Identification, Mapping, Selection and Labeling

Potential target wound identification, mapping, selection, and labeling will be performed at the Screening visit as indicated in the Schedule of Events (Table 3).

A preliminary evaluation of potential target wounds will occur at the Screening Visit. Potential wounds that meet criteria (specified below) will be identified, mapped, and labeled at Screening. **A minimum of 4 wounds should be identified if possible, to ensure the presence of at least 2 eligible wounds.** The duration of time since the wound was identified should be recorded. Additional wounds may also be identified during the Wound Monitoring Period. Upon coordination with the PI/site, these wounds may be included as potential target wounds and must have a minimum 12-week monitoring prior to dosing.

Criteria for Potential Target Wounds:

- Persistent non-healing or recurrent wounds, as per report of subject or guardian or clinical notes.
- Approximate minimum area of 5 cm² (subjects 2 to 6 years of age) or 10 cm² (subjects 7 years of age and older) and a maximum of 50 cm².
- The following wounds are excluded:
 - Wounds located on a mucous membrane, the face, hands, feet, or fully across joints.
 - Wounds that have been previously treated with a gene therapy.

Potential target wounds will be labeled by a continuous sequential number, i.e., Potential Wound 01 (P01) through Pnn.

8.3.1.2. Target Wound Selection, Mapping, Pairing and Labeling

At Day 1 (Visit 2) following the skin examination, the Investigator will select, map (i.e., location recorded by anatomic location and specific location), pair (per hierarchical criteria below) and label target wounds that meet selection criteria (specified below) based on imaging results from the Wound Monitoring Period. Depending on the size of the largest wound in the target wound pair and number of total wounds identified in the monitoring period, up to three pairs of target wounds may be identified for each subject.

Selection Criteria for Final Target Wounds:

1. Must have an approximate minimum area of 5 cm² (subjects 2 to 6 years of age) or 10 cm² (subjects 7 years of age and older) and maximum area of 50 cm²,
2. Monitored for at least 12 weeks before Day 1 (Visit 2), and wound is open (unhealed),
3. Wounds were individually isolated and did not become confluent during the Wound Monitoring Period,
4. Wounds should appear clean with adequate granulation tissue, vascularization, and not appear infected.
5. The following wounds are excluded:
 - Wounds on a mucous membrane, the face, hands, feet, or fully across joints,
 - Wounds with active infection or evidence of active infection,
 - Wounds that have been previously treated with a gene therapy intervention.

Pairing and Labeling of Final Target Wounds:

Following selection of final target wounds, the Investigator will pair the target wounds (target wound pair(s)) according to the following hierarchical criteria, and then assign the target wound pair(s) as First (Primary), Second (Secondary), and Third (Tertiary) Wound Pair(s), as applicable. The criteria to assess, in order of importance, for wounds to include in the Target Wound Pairs follow.

1. Duration of time (recorded in weeks, to the closest week) within the Wound Monitoring Period that the wound has been open immediately prior to Day 1 (Visit 2),
2. Variability of change in surface area, based on investigator's review of images in the photography vendor's imaging system, throughout the Wound Monitoring Period,
3. Size, and
4. Anatomical location.

Based on the criteria above, the wounds in the **First Wound Pair** will be wounds that:

[figure not shown]
1. Have been open for the longest duration of time immediately prior to Day 1 (Visit 2),
2. Have shown the least variability of change in surface area,
3. Are similar in size, and
4. Are similar in anatomical location.

The target wounds in the Second Wound Pair may have been open for a shorter duration, have more variability of change in the surface area and wider variation in size and anatomical location, and the wounds in the Third Wound Pair following a similar pattern of criteria.

The final selected target wound pair(s) will be ordered and labeled as follows:

1. T1A and T1B for the First Wound Pair,
 - The wound labeled as the “A” wound in each target wound pair should be superior (cephalic) in body location to the other wound in the pair which would be labeled the “B” wound. If both wounds are on the same horizontal plane, then the target wound on or toward the subject’s left-side of the body would be labeled as the “A” wound and the other wound would be labeled the “B” wound.
2. T2A and T2B for the Second Wound Pair, and
3. T3A and T3B for the Third Wound Pair.

Figure 2 provides an example of pairing and labeling wounds for a subject in which three target wound pairs are selected for inclusion in the study, and assumes the First Wound Pair has been open for the longest duration of time immediately prior to Day 1 (Visit 2), and the Third Wound Pair for the shortest time period. The First Wound Pair should be selected with the intent to fully treat the entire wound.

Figure 2: Wound Pairing, Labeling and Selection Example: Size and Location CriteriaSelection and Labeling of (Optional) Biopsy Wounds:

At selected sites only, in a subset of subjects that consent to additional research skin biopsy collection, an additional single treated wound (not from a target wound pair) may be injected with FCX-007 at Day 1 (Visit 2) and Week 12/Month 3 (Visit 3) only. This may be identified as wound BXL.

8.3.1.3. Assessment of Complete Wound Closure of Target Wounds

Investigator Assessment of Complete Wound Closure of Target Wounds must be performed by a Blinded Investigator at Weeks 12, 22, and 24 (Table 3). Blinded assessment is also preferred at Weeks 36 and 48. The assessment is to be completed after removal of subject's dressings from target wound pairs (treatment and control wounds) **and prior to any potential disruption of the target wounds** (i.e., surgical pen markings, target wound tracing, bacterial culture of wounds if applicable, FCX-007 administration preparation or administration, or collection of biopsies).

Complete Wound Closure is defined as skin re-epithelialization without drainage. Dried serous or hemorrhagic crust or other debris may be present on epithelialized wound surfaces and may include debris from adjacent wounds or dressings. Removal of the debris from the treated or control wound may cause trauma to the wound and cause removal of intact epithelium. The subject may utilize standard-of-care wound dressings and/or garments intended to protect the

wound and adjacent areas from lateral friction, and the use of such dressings does not necessarily suggest an absence of epithelium.

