12. A skin biopsy for DIF is required at Screening if: 1) subject did not previously have a skin biopsy for DIF performed and results are not contained in the subject's medical records; or 2) the subject was enrolled in a gene therapy trial for EB and did not have a skin biopsy for DIF performed following participation and results are not contained in the subject's medical records.
13. A skin biopsy for DIF is required if: 1) treated wound shows unusual inflammation (beyond temporary inflammation 1-2 days post-injection) suspected to be related to the IP, based on Investigator's judgement; or 2) a post-treatment COL7 serum antibody assay is newly positive or has a clinically significant increased titer from Screening. An unscheduled earlier visit may occur as needed.
14. A skin biopsy for hematoxylin and eosin (H&E) may be collected if: 1) an area injected with IP shows unusual growth; or 2) a DIF biopsy is being collected post-treatment and the investigator feels that the H&E biopsy will add additional information to the DIF biopsy.
15. Optional skin biopsies for IF and IEM will be collected in a subset of subjects that consent to additional biopsies. Baseline biopsies may be collected at any time prior to FCX-007 Day 1 injections and are not required if previously performed and results are contained in the subject's medical records. Biopsies at later intervals are only to be performed if there is a baseline (or prior) biopsy for same evaluations, and biopsies at Weeks 36/Month 9 (V5) and 48/Month 12 (V6) need only be obtained if the prior biopsy demonstrated COL7 expression (for IF) and/or relevant structural changes (for IEM).
16. Results must be reviewed prior to final eligibility determination on Day 1 (V2), the labs may be performed on day of visit, or within 7 days prior to this visit.
17. Blinded assessment is required at Week 12/Month 3 (V3), Week 22, and Week 24/Month 6 (V4 may be completed within 1 day prior to the visit if this is still within the Week 24 Visit window and does not interfere with the time from the Week 22 assessment).
18. Wound assessment (WA) at Week 22 may be performed via remote video assessment, assessment of adequate and current wound imaging, or during a clinic visit.
19. At Week 24/Month 6 (V4) and Week 36/Month 9 (V5) unclosed treatment wounds may be re-treated and unclosed control wounds may be injected.
20. May be completed within 1 day prior to the visit unless otherwise noted.

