8.5.2.2. Phone Call Assessments

A 3-day post-injection phone call is required following any visit where a subject has received FCX-007 injections.

In addition, phone calls are required midway between visits.

8.5.2.3. Wound Assessment at Week 22

The Blinded Investigator Assessment of the target wounds is expected to be conducted via remote video assessment (telemedicine), assessment of adequate and current (same day) wound imaging, or during a clinic visit.

The Blinded Investigator is only to assess closure of the wound(s) and should instruct the subject or their legal and/ to discuss other issues (e.g., AEs, concomitant medications, visit schedule) with other clinical study personnel.

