13.3. APPENDIX 3: INVESTIGATIONAL PRODUCT ADMINISTRATION INSTRUCTIONS

Intradermal injections of IP are to be administered by the PI or, if necessary, an appropriately trained physician Sub-I.

1. Premedicate/Administer anesthesia.
 - Subjects will be administered anesthesia per standard of care at the investigative site. To minimize pain and discomfort during the IP administration, the Investigator should determine the most appropriate anesthetic for each subject, including the use of topical anesthetic cream, local anesthesia, conscious (moderate) sedation, general anesthesia (if undergoing another procedure at time of injection) or a combination thereof.
 - In addition, medication should be considered during and after the injections to treat pain and/or anxiety (e.g., lorazepam).
2. Perform the FCX-007 Administration Preparation procedures (refer to Section 9.7.1).
3. Approximately 15 minutes prior to the administration of FCX-007, remove the subject's treatment vials from the shipper.
4. Resuspend the cells by gently inverting the injection vial three (3) times.
5. Tap the top of each vial to release any fluid in the cap prior to opening the vials. Do not dilute the product.
6. Unscrew the cap and, using a detachable bore (such as 21-gauge needle, or the hub of the sterile syringe), aseptically draw 1.0 mL from one vial. NOTE: Living cells are fragile and should be handled gently, especially when being aspirated into a syringe. Go slowly and use care during this process.
7. Once the product is in the syringe, remove the 21-gauge needle, if applicable, and replace it with the 30-gauge needle for injection of the product. **Do not use a 21-gauge needle for injection of the product.** Follow sterile technique during this process.
8. Hold the syringe using the proper technique: the bevel facing upwards and the arms of the syringe are vertical. Some clinicians may prefer to bend the needle upwards at about a 15-degree angle to facilitate staying in a superficial plane — but use of this technique is optional. Grip the syringe with the middle and index finger below the syringe arms, placing the thumb on the upper arm of the syringe. Do not place the thumb on the plunger while directing the needle into the skin to avoid premature discharge of the product.
9. Insert the 30-gauge needle at the pre-identified and marked injection site.

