6.7.3 Supportive Efficacy Analysis

Durability of wound closure from Week 24 through Week 48 is defined as a wound assessed as closed at Week 24 (with confirmatory closure at Week 22), as well as closed at the Week 36 and Week 48 WA. Summaries will be done for both First wounds and all qualifying wounds (those assessed as closed at Week 24) by treatment group.

Durability of wound closure from Week 24 through Week 36 is defined as a wound assessed as closed at Week 24 (with confirmatory closure from Week 22), as well as closed at the Week 36 WA. Summaries will be done for both First wounds and all qualifying wounds (those assessed as closed at Week 24) by treatment group.

Durability of wound closure from Week 12 through Week 48 is defined as a wound assessed as closed at Week 12, as well as closed at Weeks 24 (with confirmatory closure at Week 22), 36 and 48 WAs. Summaries will be done for both First wounds and all qualifying wounds (those assessed as closed at Week 12) by treatment group.

Durability of wound closure from Week 12 through Week 36 is defined as a wound assessed as closed at Week 12, as well as closed at Weeks 24 (with confirmatory closure at Week 22) and 36 WAs. Summaries will be done for both First wounds and all qualifying wounds (those assessed as closed at Week 12) by treatment group.

The Wong-Baker FACES Pain Rating Scale will be summarized by visit with changes from Baseline at Weeks 12, 24, 36 and 48. Summaries will be done for the First wound pair, and all wound pairs, as well as by maximum across wounds (treated and control).

COL7 expression in treated wounds as assessed by IEM and IF at Weeks 36 and 48 will be presented in listings.

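### The Week 36 and Week 48 closure readings, which decide persistence in all four durability endpoints, are not required to be blinded

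*Protocol*

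**What the plan says.** Protocol 8.3.1.3 sets two standards for the same assessment. For the earlier visits, "Investigator Assessment of Complete Wound Closure of Target Wounds must be performed by a Blinded Investigator at Weeks 12, 22, and 24". For the later ones, "Blinded assessment is also preferred at Weeks 36 and 48". Protocol 8.3.1 and SAP 4.1.3 say the same. Table 3 note 17 is consistent with this: "Blinded assessment is required at Week 12/Month 3 (V3), Week 22, and Week 24/Month 6". The closure row of Table 3 does not carry that note at Visits 5 and 6.

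SAP 6.7.3 builds the durability endpoints on those later visits. Durability from Week 24 through Week 48 needs confirmed closure at Week 24 and then the wound "as well as closed at the Week 36 and Week 48 WA"; through Week 36 it needs the wound "as well as closed at the Week 36 WA". The two endpoints that start at Week 12 add a Week 12 closure and otherwise use the same readings.

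On who is unblinded, Protocol 8.3.1 describes the PI or Sub-I who selects and labels the wounds as one "who will remain unblinded to wound treatment assignment throughout the study". Appendix 3 adds: "Intradermal injections of IP are to be administered by the PI or, if necessary, an appropriately trained physician Sub-I". Neither document names the reader for a Week 36 or Week 48 assessment that is not done blind.

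**The concern.** Closure is a visual judgement. Protocol 8.3.1.3 lets crust and debris remain on a closed wound and warns that removing them may damage the epithelium. Control wounds are untreated and receive no placebo injection (Protocol 6.2), so anyone who knows the assignment knows which wound is expected to do better. The protocol treats this as reason enough to mandate blinding through Week 24, and the judgement is no different at Weeks 36 and 48.

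If blinding lapses at the later visits, a durability result combines blinded qualifying readings with unblinded persistence readings, and the output would not show where this happened. The documents do not require the reader's blinding status to be recorded. The sensitivity analyses in SAP 6.7.5 concern missing data only, and SAP 6.7.4 sends the imaging data to listings. The durability endpoints are the planned summaries of closure after Week 24, so how long closure lasts would be judged from these figures.

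**Working it through.** **The plan's own figure.** The documents give no figure for durability. The only design figure is 85% power for the primary endpoint with 24 pairs (Protocol 10.2). An exact two-sided McNemar test, averaged over a Binomial(24, 0.70) number of discordant pairs with probability 0.60/0.70 that the treated wound is the closed one, gives 85.1%. The figure reproduces, and blinding at Weeks 36 and 48 does not alter it.

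**Which readings are exposed.** Taking the SAP 6.7.3 definitions against the blinding rule:

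| Durability endpoint | Readings needed (weeks) | Not required blind | Share |
|---|---|---|---|
| Week 24 to 48 | 22, 24, 36, 48 | 36, 48 | 2/4 |
| Week 24 to 36 | 22, 24, 36 | 36 | 1/3 |
| Week 12 to 48 | 12, 22, 24, 36, 48 | 36, 48 | 2/5 |
| Week 12 to 36 | 12, 22, 24, 36 | 36 | 1/4 |

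All four endpoints contain at least one exposed reading, and none consists only of exposed readings.

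**Do the late readings still bear on the randomised comparison?** Yes. Only unclosed wounds may be injected at Weeks 24 and 36 (Protocol 9.1), while every durability definition requires closure at Week 24. Under the plan, a control wound that can still count as durable has therefore not been injected at Week 24. One found open at Week 36 has already failed. Optional injection of control wounds does not make the late readings moot.

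**Sensitivity to one reading.** SAP 7 gives 6 enrolled subjects.

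- First wounds, 6 per arm: 1/6 = 16.7 points. At the planned 24 it would be 1/24 = 4.2 points.
- If the denominator is wounds closed at Week 24, the planning rates give 0.60 × 6 = 3.6 treated and 0.10 × 6 = 0.6 control First wounds. Assuming 4 of 6 treated wounds qualify, one reading is worth 1/4 = 25 points.

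**Illustration of bias, on assumed values that are not in the documents.** Among qualifying wounds, let the true chance of being closed at each late visit be r in both arms. Let an unblinded reader call a fraction f of reopened treated wounds closed, make no error on controls, and err independently at each visit. The false treatment difference is:

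- one late visit: (1 − r)f
- two late visits: (r + (1 − r)f)² − r²

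| r | f | One visit | Two visits |
|---|---|---|---|
| 0.70 | 0.05 | 0.015 | 0.511 − 0.490 = 0.021 |
| 0.70 | 0.20 | 0.060 | 0.578 − 0.490 = 0.088 |
| 0.50 | 0.05 | 0.025 | 0.276 − 0.250 = 0.026 |
| 0.50 | 0.20 | 0.100 | 0.360 − 0.250 = 0.110 |

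Over r = 0.5 to 0.7 and f = 0.05 to 0.20 the false difference is 1.5 to 10 points with one visit and about 2 to 11 points with two.

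**Extra workload.** 6 subjects × 2 visits = 12 subject-visits at most.

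**The case against.** The strongest reply is that this is a deliberate and consistent choice. The two documents agree, and blinding is mandatory for every reading behind the primary and secondary endpoints. Durability is supportive, and Protocol 10.4.2.3 calls any testing of it exploratory. The SAP now does no testing at all. This stands: type I error, power and the main results are untouched.

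A reader might infer that durability as a whole rests on the unblinded injector. The documents do not support that. Every durable wound must first be judged closed by a blinded reader at Weeks 22 and 24, so a late unblinded reading cannot rescue a wound read as open then. At the planning rates only about 0.6 control First wounds would qualify, so much of any difference between arms would already be fixed by the blinded readings. The exposed part is mainly the persistence figure for treated wounds. That the fallback reader is the injector is also an inference: the text permits it but does not say it.

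A reader might also infer that the late readings are made with the Week 24 primary results in hand. SAP 6.1 and 6.1.6 say only that the primary analysis follows completion and cleaning of all subjects' Week 24 data. Earlier subjects could reach Week 36 or 48 before then, and nothing says that results go to the sites. The point does not depend on this.

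There is a partial safeguard. Site images of both wounds at Weeks 36 and 48 are taken before any disturbance, timestamped and checked for tracing accuracy (Protocol 8.3.2). They allow a doubtful call to be examined, but no planned summary uses them to check closure.

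Finally, a strict requirement could turn an available reading into a missing one in a very small study. That is a fair objection to a bare requirement, and the fix below allows for it.

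**Conclusion.** The point holds for the persistence component of the durability endpoints: Week 36 in all four and Week 48 in two. A site can follow the plan exactly and still have these readings made by someone who knows the assignment, and the report would not show it. The 16.7 points per First wound would apply to any misread wound at this sample size, so it measures fragility and not bias. The 1.5 to 11 points rest wholly on assumed error rates. The documents give no rate of biased reading and do not show how often the stated preference was met; if it was always met, no reading was exposed. This is a modest weakness, worth correcting because the percentages are themselves the reported result and the Blinded Investigator role already exists.

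**What to change.** 1. In Protocol 8.3.1, 8.3.1.3, Table 3 note 17 and SAP 4.1.3, make blinded assessment required at Weeks 36 and 48. Use the existing Blinded Investigator at the scheduled visit. As fallback, allow the route already accepted at Week 22 in Protocol 8.5.2.3: remote video or "assessment of adequate and current (same day) wound imaging".
2. If a blinded reading cannot be obtained, keep the unblinded one. Record the reader's blinding status on the CRF for every Week 36 and Week 48 reading.
3. In SAP 6.7.3, report durability overall and from blinded readings only.
4. For visits already completed, apply the recording and reporting steps alone.

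The cost is some time from the existing blinded assessor, for at most 12 subject-visits, with no new visit or role. The remaining drawback is that image or video readings at Weeks 36 and 48 may be mixed with in-person readings.
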